13.1. Efficacy Analysis

13.1.1. Analysis Populations

The following subject populations will be evaluated and used for presentation and analysis of the data:

- The Intent-to-Treat (ITT) Population will include all randomized subjects who receive any amount of investigational product (OCA or placebo). The ITT Population will be the primary population used for efficacy analyses. Treatment assignment will be based on the randomized treatment.
- The Safety Population will include all subjects who received any amount of investigational product (placebo or OCA). The Safety Population will be the primary population used for safety analyses. Treatment assignment will be based on the treatment actually received.
- The PK population will include all OCA subjects who have at least one confirmed fasted analyzable sample. Subjects must have been fasting for approximately 8 hours prior to the visit and must not have any major protocol deviations that potentially affect exposure levels. The PK population will be used for OCA PK analyses.
- The Overall Historical Control Population will include subjects from the United Kingdom (UK) -PBC Group and Global PBC Study Group databases with demonstrated comparability to randomized subjects in this clinical study (747-302) with respect to both subject characteristics and disease progression.
- The UK-PBC Historical Control Population will include subjects from the UK-PBC Group databases with demonstrated comparability to randomized subjects in this clinical study (747-302) with respect to both subject characteristics and disease progression.
- The Global PBC Historical Control Population will include subjects from the Global PBC Study Group database with demonstrated comparability to randomized subjects in this clinical study (747-302) with respect to both subject characteristics and disease progression.

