13.1.3. Primary Efficacy Analysis

The primary efficacy endpoint will be the time to first occurrence of one of the following post-randomization:

- Death (all-cause)
- Liver transplant

- MELD score ≥ 15
- Hospitalization (as defined by a stay of 24 hours or greater) for new onset or recurrence of:
 - Variceal bleed
 - Hepatic encephalopathy (as defined by a West Haven score of ≥ 2)
 - Spontaneous bacterial peritonitis (confirmed by diagnostic paracentesis)
- Uncontrolled ascites (diuretic resistant ascites requiring therapeutic paracentesis at a frequency of at least twice in a month).
- Hepatocellular carcinoma confirmed by 2 complimentary imaging modalities unless confirmed by biopsy

The primary efficacy analysis will compare randomized OCA to randomized placebo with respect to the primary efficacy endpoint using the ITT population. Only adjudicated events will be included in analyses. The 2 treatment groups will be compared using the log rank test stratified by the randomization stratification factor. Kaplan-Meier (KM) estimates of the distribution of the time-to-event will be tabulated and graphed by treatment group. The tabulation will include the KM estimate of the medians and corresponding 95% confidence intervals (CIs), if the medians can be estimated. The number and percent of subjects censored and with events will be presented. The hazard ratio and 95% CI will be determined based on a Cox regression model stratified by randomization strata to estimate the magnitude of the effect.

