13.1.9. Handling of Dropouts or Missing Data

Subjects who discontinue investigational product are expected to continue in the study until study termination.

Missing data will be assumed to be missing at random. In order to determine the effect of missing data on the analysis, efficacy endpoints will be analyzed using different methods of imputation as described below.

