13.1.9.1. Time to Event Endpoints

For the time to event analyses, subjects who do not experience an event will be censored at the time of their last contact. Subjects with no data after randomization will be considered to have an event on Day 1 (first day of investigational product dosing).

For analyses of the percentage of subjects with an event, subjects with no data after randomization will be considered to have an event.

All time to event endpoints include only adjudicated events. Sensitivity analyses may consider all events regardless of adjudication. Events with discrepant adjudication will be analyzed using both results.

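### Scoring subjects with no post-randomization data as Day 1 events contradicts the adjudicated-events-only rule and can move the hazard ratio either way

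*Protocol*

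**What the plan says.** Section 13.1.9.1 gives two rules for subjects without an observed event. In general, "subjects who do not experience an event will be censored at the time of their last contact". The exception is: "Subjects with no data after randomization will be considered to have an event on Day 1", with Day 1 defined as the first dosing day. A further sentence counts the same subjects as having an event when percentages with an event are analysed.

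The section also says "All time to event endpoints include only adjudicated events". Section 13.1.3 repeats this for the primary endpoint: "Only adjudicated events will be included in analyses". Section 13.4 requires blinded committee review, based on source documents, before an event enters any analysis.

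Two other statements bear on the point. Section 13.1.9 says "Missing data will be assumed to be missing at random". Section 13.1.1 limits the primary population to dosed subjects: "The Intent-to-Treat (ITT) Population will include all randomized subjects who receive any amount of investigational product".

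All of this is Version 3.1 text. The file also holds the start of Version 4 (10 May 2017). Its table of contents keeps the heading 13.1.9.1, but the text under it is not shown.

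**The concern.** For a subject with no follow-up, the Day 1 rule and the adjudication rule cannot both be obeyed. There is no occurrence and no source document for a committee to review, and the section has no carve-out saying which rule prevails.

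The rule is also an informative imputation inside a plan that otherwise assumes missingness at random. A subject last contacted at Month 1 is censored there. A subject lost just before Month 1 is scored as having died, been transplanted or decompensated on Day 1. The rule has no cause-specific limit, so one such subject takes an event on every time-to-event endpoint. The two key secondary time-to-event endpoints (MELD score of 15 or more; transplant or death) are parts of the composite and cannot have more real events than it has, so each assigned event will generally weigh more there.

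At stake is the primary hazard ratio: it is diluted if such subjects are balanced between arms, and shifted in either direction if they are not.

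**Working it through.** **Inputs from the protocol.** Section 13.1.2: placebo event-free proportion 0.6 at 8 years, hazard ratio 0.60, 2-sided 5% log-rank test, 1:1 allocation, 4 years accrual plus 6 years follow-up, 127 events, 80% power, 428 subjects. Section 13.1.12: interim looks at 50% and 75% of events with Lan-DeMets O'Brien-Fleming boundaries. Version 4 synopsis: 10% dropout.

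**Input not in the protocol.** The number of analysed subjects with no post-randomization data. It is assumed below and shown as a range.

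**Step 1: reproduce the plan's figures.**
- Freedman: [(1 + 0.6)/(1 − 0.6)]² × (1.960 + 0.842)² = 16 × 7.85 = 125.6, so 126 events.
- Schoenfeld: 4 × 7.85/(ln 0.6)² = 120.3, so 121; about 123 with the two interim looks. Power at 127 events is 81.4% with the looks and 82.1% for a fixed design.
- Hazards: −ln(0.6)/8 = 0.0639 per year on placebo and 0.6 × 0.0639 = 0.0383 on OCA. Event probability 1 − [exp(−6λ) − exp(−10λ)]/(4λ) is 0.398 on placebo and 0.263 on OCA, mean 0.331. Then 127/0.331 = 384, and 384/0.9 = 427, against the stated 428.

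The 127 and 428 are therefore sound. The point concerns only the missing-data rule.

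**Step 2: score approximation.** Add a Day 1 events on OCA and b on placebo to 127 real events. The log-rank score is U = (127/4) ln 0.6 + (a − b)/2, its variance is V = (127 + a + b)/4, the hazard ratio is exp(U/V), and power is Φ(−U/√V − 1.96). Here (127/4) ln 0.6 = −16.22.
- Four per arm: U = −16.22, V = 33.75, hazard ratio exp(−0.481) = 0.618, power 0.80.
- Four on OCA only: U = −14.22, V = 32.75, hazard ratio exp(−0.434) = 0.648, power 0.70.
- Four on placebo only: U = −18.22, V = 32.75, hazard ratio exp(−0.556) = 0.573, power 0.89.

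Balanced additions raise V without changing U, which is pure dilution. Unbalanced additions move U directly.

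**Step 3: Cox simulation.** 214 per arm, the hazards above, uniform accrual, 10% dropout, cut-off at the 127th real event, critical value 1.96, 4,000 runs per row. Monte Carlo error on power is about √(0.8 × 0.2/4000) = 0.6 points. Each cell gives hazard ratio, then power.

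| No-data subjects, OCA/placebo | Event on Day 1 | Censored |
|---|---|---|
| 0/0 | 0.599, 0.81 | 0.599, 0.81 |
| 2/2 | 0.608, 0.81 | 0.599, 0.82 |
| 4/4 | 0.617, 0.80 | 0.598, 0.81 |
| 6/6 | 0.626, 0.80 | 0.598, 0.82 |
| 10/10 | 0.642, 0.77 | 0.598, 0.82 |
| 4/0 | 0.648, 0.69 | 0.598, 0.81 |
| 0/4 | 0.573, 0.88 | 0.601, 0.81 |
| 8/0 | 0.700, 0.54 | 0.599, 0.81 |
| 0/8 | 0.543, 0.94 | 0.597, 0.82 |

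The two methods agree closely. For four per arm the power loss is 1.7 points by simulation (0.812 to 0.795) and 2.4 by the approximation (0.821 to 0.797). Four subjects are 4/428 = 0.9% of the sample.

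**The case against.** The strongest defence is that the rule has almost nobody to act on. The analysis set requires a dose, and Sections 9.1 and 9.7.7 place the first dose on the day after the randomization visit. A subject with no later data normally has no diary, tablet count or contact to show that a dose was taken, and so would normally fall outside the set. Any later visit, telephone call or record review counts as data and moves the subject to ordinary censoring. This stands: the distortion is a conditional risk of unknown and probably small size. It does not resolve the contradiction between the two rules.

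A second defence is that scoring missing subjects as failures is conservative. That holds if the losses are balanced or fall mainly on OCA. It fails if they fall mainly on placebo.

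A reader might go further in four ways that the document does not support.
- That the assigned events would help trigger the interim or final analyses. Sections 7.1, 7.2, 7.5 and 13.1.2.1 define the 127 as adjudicated events, which these are not. The wording for the interims in Section 13.1.12 is looser, but it does not call for counting imputed events.
- That early pruritus on OCA makes a large imbalance likely. A subject known to have stopped for pruritus has post-randomization data, so the rule does not apply, and Section 8.4.3 expects subjects who stop treatment to stay in the study.
- That the larger shifts in the table are expected. They rest on imbalances that nothing in the protocol predicts.
- That the ITT set must be redefined as all randomized subjects. That is a separate question and is not needed to cure this one.

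**Conclusion.** As written in Version 3.1, the rule is wrong: it contradicts the adjudication requirement in its own section and in Section 13.1.3, and it departs from the missing-data assumption and the censoring rule beside it. Its effect depends on a count that the protocol does not give and that should be small.

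Under a true hazard ratio of 0.60, small balanced counts cost 1 to 3 points of power. Four subjects in one arm only move the hazard ratio to about 0.65 or 0.57, depending on the arm. Censoring keeps it at about 0.60 in every case tried. This should be fixed before unblinding, but it does not threaten the trial. Confidence is moderate, mainly because the Version 4 wording of Section 13.1.9.1 is not shown and the rule may already have been changed.

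**What to change.** First confirm whether Version 4 keeps the rule. If it does:
- In Section 13.1.9.1, censor subjects with no post-randomization data at randomization (Day 0, or Day 1 if the time scale starts there) in the primary analysis and the other time-to-event analyses. They then add no event and essentially no follow-up time.
- Replace the matching sentence for percentages with an event: keep these subjects in the denominator as having no observed event. Deleting the sentence alone would leave them without a rule.
- If the sponsor wants the present rule shown, keep it only as a labelled extreme-case sensitivity analysis, and report the number of such subjects by arm.

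The cost is two changed sentences in the protocol, mirrored in the SAP, and one optional sensitivity table. No new data are needed, and the 127 events and 428 subjects are unaffected.

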13.1.9.2. Quantitative Endpoints

For efficacy endpoints that utilize an ANCOVA model, observed cases will serve as the primary analysis. Sensitivity analyses to assess the effect of missing data may be conducted where missing data is imputed using last observation carried forward.

Sensitivity analyses of ANCOVA models will also be evaluated using a restricted maximum likelihood based mixed-effect repeated measures model where no imputations will be made for missing values.

13.1.9.3. Responder Endpoints

In an efficacy analysis in which subjects are classified as either a responder or a non-responder (binary outcome) based on dichotomizing a continuous variable, any subject who does not provide an assessment at the specified time point for the defining of response will be considered to be a non-responder. That is, for the percentage of responders, the subject will be included in the denominator and will not contribute to the numerator.

For sensitivity analyses using only “observed cases,” subjects who do not provide an assessment at the specified timepoint for the defining of response will not be included. That is, for the percentage of responders, the subject will not be included in the numerator or the denominator.

13.1.10. Multiple Comparisons/Multiplicity

The key secondary efficacy endpoints are as follows:

- Time to MELD score ≥ 15
- Time to first occurrence of liver transplant or death (all-cause)
- Change from Baseline in total bilirubin at end of study
- Change from Baseline in ALP at end of study

The hypothesis testing of key secondary analyses will compare placebo and OCA and will be conducted in a sequential closed testing gate-keeping procedure (in the order in which the key secondary endpoints are stated above), provided that the primary efficacy endpoint comparison is statistically significant in favor of OCA. If the primary comparison is not statistically significant then comparison of the secondary endpoints will be considered as descriptive and exploratory. This procedure controls the study-wise type I error.

- First (step 1) placebo and OCA will be compared with respect to the primary efficacy endpoint. If the comparison achieves statistical significance at 2-sided 0.05 level in favor of OCA group, then
- The time to MELD score ≥ 15 will be compared between placebo and OCA (step 2). If the comparison achieves statistical significance at 2-sided 0.05 level in favor of OCA group, then
- The time to liver transplant or death (all-cause) will be compared between placebo and OCA (step 3). If the comparison achieves statistical significance at 2-sided 0.05 level in favor of OCA group, then
- Change from Baseline in total bilirubin will be compared between placebo and OCA (step 4). If the comparison achieves statistical significance at 2-sided 0.05 level in favor of OCA group, then
- Change from Baseline in ALP at the end of study will be compared between placebo and OCA (step 5).

If at any step defined above the comparison is not statistically significant at the 2-sided 0.05 level then the remaining comparisons in the stated hierarchy will be considered descriptive and exploratory. The study-wise type I error will be maintained with the above closed procedure.

Additional efficacy endpoints will be analyzed; however, hypothesis tests will be applied for descriptive and exploratory purposes only.

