13.1.12. Continuous Monitoring and Interim Analyses

Blinded safety reports including the accrual of events, drop outs and/or loss of patients to commercially available OCA will be reviewed by the DMC on a regular basis.

Two planned interim analyses of the liver-related outcomes will be conducted using the Lan-DeMets O'Brien-Fleming boundaries ([Reboussin 2000](#)). Both interim analyses will be pre-specified and will occur after accrual of 50% and 75% of clinical outcome events, respectively.

The DMC will review the available efficacy data in conjunction with detailed safety data and other relevant information to recommend continuation, modification, or cessation (for efficacy or futility) of the study beyond each interim analysis. Modification of the study would not take place without prior agreement with regulatory authorities.

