APPENDIX G. SUMMARY OF CHANGES: PROTOCOL VERSION 3.1 (DATED 23 DECEMBER 2016)

Rationale and Summary of Changes

Major revisions to Protocol 747-302 include the expansion of the spectrum of stages of PBC disease, the addition of progression to cirrhosis as a secondary endpoint, and the addition of two interim analyses. Additional revisions include an increase in subject number and the number of required clinical outcome events, a change in the study phase, an update to the nomenclature for PBC, and various clarifications within the protocol.

The following table includes revisions that were made to Protocol Version 3.1 with an associated reason or justification for the change. Rationales (Justifications for Change) that impact multiple sections are provided below and referenced in the table with the appropriate rationale number.

1. The phase of the study has been changed from '3b' to '4' to reflect that this is a post-marketing study.
2. The term 'primary biliary cirrhosis' has been changed to 'primary biliary cholangitis' throughout the document to reflect recent changes in nomenclature for PBC.
3. The increase in number of required events from 121 to 127 is due to the addition of two interim analyses (IA), which will allow an independent DMC to recommend continuation, modification, or cessation (for efficacy or futility) of the study. One IA will occur at 50% information (after 64 events occur) and one at 75% information (after 96 events occur). Inclusion of patients with earlier stage disease will also increase the time to event requiring more events in order to keep follow-up to approximately 6 years.
4. The first year study enrollment rate was lower than projected due to slower-than-anticipated activation of sites and required a re-estimation of the accrual duration. Using observed accrual rates, the accrual duration was extended by two years. The follow-up period was maintained at 6 years, thereby leading to a total trial duration of 10 years.
5. 'Encephalopathy' has been modified to 'Hepatic Encephalopathy' to clarify that the relevant clinical outcome enApdpoint should be related to hepatic disease.
6. Histological confirmation (biopsy) has been added as an acceptable method of confirming a diagnosis of Hepatocellular Carcinoma.

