- The 2 groups will be compared using a 2-sided log rank test at the 5% level of significance.
- Two interim analyses and one final analysis are planned. The first interim analysis will be performed when 50% of the target events are accrued and the second interim will be performed when 75% of the target events are accrued.
- A dropout rate of 10% is assumed.

Based on the randomization ratio, significance level, and assumed hazard ratio, a total of 127 events (both groups combined) will provide 80% power to demonstrate a statistically significant difference between OCA and placebo on time to liver-related outcomes, including all-cause mortality.

In addition, based on the remaining assumptions stated above, it is estimated that approximately 428 subjects will be enrolled to attain 127 events.

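### Section 13.1.10 sets the primary and every key secondary at 2-sided 0.05 without regard to the two efficacy looks in 13.1.12, so the final threshold is ambiguous and the key secondaries are unprotected at an early stop

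*Protocol*

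**What the plan says.** Section 13.1.10 (Multiple Comparisons/Multiplicity, Version 3.1) lists five ordered steps. Step 1 reads "placebo and OCA will be compared with respect to the primary efficacy endpoint. If the comparison achieves statistical significance at 2-sided 0.05 level" in favour of OCA, after which testing moves to time to MELD score of 15 or more, time to transplant or death, change in bilirubin, and change in ALP. The stopping rule has the same level: "If at any step defined above the comparison is not statistically significant at the 2-sided 0.05 level", the remaining comparisons become descriptive. The section states twice that error is controlled, the second time as "The study-wise type I error will be maintained with the above closed procedure". It mentions neither the interim analyses nor any alpha already spent.

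Section 13.1.12 says "Two planned interim analyses of the liver-related outcomes will be conducted using the Lan-DeMets" O'Brien-Fleming boundaries, and that these looks "will occur after accrual of 50% and 75% of clinical outcome events, respectively". The Data Monitoring Committee may "recommend continuation, modification, or cessation (for efficacy or futility) of the study beyond each interim analysis". No final nominal level is given, and nothing is said about testing key secondaries at an early stop.

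Section 13.1.2 and both synopses give the design level: "The 2 groups will be compared using a 2-sided log rank test at the 5% level of significance", listed beside two interim analyses and one final analysis. The Version 3.1 change rationale in Appendix G puts the looks at 64 and 96 events and attributes the rise from 121 to 127 events to them.

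**The concern.** An alpha-spending boundary uses part of the 5% at the interim looks, so less than 5% remains for the final one. A hierarchy that declares the primary significant at 0.05 without mentioning those looks appears to spend that part twice. Two sections of one protocol could then give opposite confirmatory answers to the same final p-value.

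The key secondaries raise a second question. Time to MELD score of 15 or more and time to transplant or death are built from components of the primary composite, so their test statistics should be positively correlated with it. If the trial stops when the primary crosses early, the moment of testing has been chosen by data that also favour the secondary. An unadjusted 0.05 at that moment does not hold the error at 5%, even when the primary boundary is right.

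Section 5.5.1 describes the trial as designed to confirm clinical benefit after a surrogate-based Phase 3 study. Its success rule should have one meaning before any unblinded look.

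**Working it through.** **Inputs.** Overall 2-sided 5%, 1:1 allocation, hazard ratio 0.60, 127 events, 80% power (13.1.2); looks at 50%, 75% and 100% with Lan-DeMets O'Brien-Fleming boundaries (13.1.12); 64 and 96 events at the interims (Appendix G), so information fractions 64/127 = 0.504 and 96/127 = 0.756. The protocol does not say whether the 5% is spent as two one-sided 0.025 boundaries or directly as one 2-sided 0.05, so both are shown.

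**1. The plan's own figure.** For a fixed design:
- Schoenfeld: 4(1.960 + 0.842)² / (ln 0.60)² = 121 events.
- Freedman: (1.960 + 0.842)² × (1.6/0.4)² = 126 events.

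The three-look design inflates these by 1.020 (two one-sided) to 123 and 129, or by 1.031 (direct) to 125 and 130. The stated 127 lies inside that range.

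**2. Boundaries.** Cumulative 2-sided alpha spent by information fraction t:
- two one-sided 0.025: 4[1 − Φ(2.241/√t)], which is 0.0031 at t = 0.5 and 0.0193 at t = 0.75;
- direct 2-sided 0.05: 2[1 − Φ(1.960/√t)], which is 0.0056 and 0.0236.

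The critical values follow from the joint normal distribution of the three statistics, with correlation √(tᵢ/tⱼ). The last column replaces the correct final critical value by 1.960, as 13.1.10 reads literally: 1 − P(|Z₁| < c₁, |Z₂| < c₂, |Z₃| < 1.960).

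| Spending form | Looks | Nominal 2-sided levels | Overall error with 0.05 at the final look |
|---|---|---|---|
| Two one-sided 0.025 | 50/75/100% | 0.0031, 0.0183, 0.0440 | 0.0554 |
| Two one-sided 0.025 | 64/96/127 events | 0.0032, 0.0189, 0.0438 | 0.0555 |
| Direct 2-sided 0.05 | 50/75/100% | 0.0056, 0.0216, 0.0411 | 0.0577 |
| Direct 2-sided 0.05 | 64/96/127 events | 0.0058, 0.0220, 0.0409 | 0.0578 |

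**3. Power with the correct boundaries at 127 events.** The Schoenfeld drift is √(127/4) × |ln 0.60| = 2.88, giving 0.813 (two one-sided) or 0.809 (direct). The Freedman drift is √127 × 0.4/1.6 = 2.82, giving 0.797 or 0.792.

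**4. Key secondaries.** Simulation with the primary on the correct two one-sided boundary (z = 2.963, 2.359, 2.014), the first key secondary truly null, and that secondary tested at z > 1.960 at the look where the primary first crosses. The correlation and the size of the primary effect are assumptions, since the protocol gives no correlation. The highest one-sided error over the primary effects tried, against 2.5%:

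| Assumed correlation | Highest one-sided error |
|---|---|
| 0.5 | 2.8% |
| 0.7 | 3.0% |
| 0.8 | 3.2% |
| 0.9 | 3.4% |

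The excess fades as the primary effect grows. At correlation 0.8 it is nearly gone (0.0503 on the doubled scale) at a drift of 5.

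**The case against.** The strongest reply is that 0.05 means the overall group-sequential level. Section 13.1.2 lists the 5% test and the two interims as assumptions of one calculation, 13.1.12 names boundaries that fix the final critical value once overall alpha is known, and the event count was raised because of the looks. On that reading the primary is controlled. This stands, and it is why a reader who infers that error control for the primary has simply failed would go too far. It does not remove the need for a change: 13.1.10 attaches 0.05 to each comparison, and 13.1.10 and 13.1.12 do not refer to each other.

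A second reply is that final nominal levels and interim handling of secondaries belong in the SAP. Silence would be acceptable on that ground. Here the protocol states a level and claims control, so an SAP using about 0.044 would depart from the protocol's literal rule.

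Third, 13.1.12 does not say that the hierarchy is run at an interim, and two key secondaries are defined at end of study. This also stands in part: the secondary inflation arises only if the trial stops early and the secondaries are tested then. But the hierarchy opens whenever the primary is significant, and 13.1.12 allows an efficacy stop.

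Fourth, the 13.1.10 quoted is Version 3.1. Version 4's own 13.1.10 is listed in its table of contents but not shown. Its synopsis keeps the 5% test, the gatekeeping and both interims, and gives no level for each step. One cannot say that Version 4 repeats the wording, only that it needs checking.

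A reader might also infer an overall error near 10%, since 0.05 at all three looks would give 0.097. The document does not support that, because 13.1.12 puts spending boundaries on the interims. Nor is the event count at fault.

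**Conclusion.** The point holds as a defect in how the decision rule is written. Taken literally, 13.1.10 gives an overall 2-sided error for the primary of about 0.055 to 0.058, and leaves a band of final p-values, from about 0.041 or 0.044 up to 0.05, that is a success in one section and a failure in the other. Taken as an overall level, 0.05 protects the primary. The claim of study-wise control still fails for key secondaries tested at an unadjusted 0.05 after an interim crossing, with one-sided error up to about 2.8% to 3.4%.

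The primary figures depend on the unstated spending form and on looks close to plan. The secondary figures are worst cases over primary effect size, under assumed correlations of 0.5 to 0.9, and apply only at an early stop. The inflation is modest, but it sits in the confirmatory rule.

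**What to change.** In 13.1.10, and in the current version's equivalent if it carries the same wording:

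- State that 0.05 is the overall 2-sided level across all looks.
- State that the primary is significant only if it crosses the Lan-DeMets O'Brien-Fleming boundary at that look, computed from the actual information fraction. Name whether alpha is spent as two one-sided 0.025 or one 2-sided 0.05. The final nominal level then comes out at about 0.044 or 0.041, and should be calculated, not hard-coded.
- State that, if the primary crosses at an interim, each key secondary tested then is compared with a pre-specified alpha-spending boundary whose overall level is 0.05, not with an unadjusted 0.05. An O'Brien-Fleming-type boundary is one option. The protocol gives no planned event totals for the time-to-event secondaries, so how their information is measured must also be specified.
- Cross-refer 13.1.10 and 13.1.12.

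The cost is a slightly stricter final threshold and stricter secondary thresholds at an early stop (about 0.003 to 0.006 at the first look under an O'Brien-Fleming shape at 50% information). No change in events or sample size is needed: 127 events give 79% to 81% power depending on formula and spending form.
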